8.6. Other Safety Evaluations

8.6.1. Vital Signs

Vital signs include: respiratory rate (breaths/minute); temperature (°C); and pulse rate (beats/minute). Note that systolic and diastolic blood pressure will be summarized with the other anthropometric parameters. Observed values and changes from baseline for vital signs will be summarized at each visit and time point, as well as for most extreme change from baseline. Summaries will be provided for the safety population and displayed by treatment group.

8.6.2. Electrocardiogram (ECG)

Electrocardiogram (ECG) parameters include: HR (bpm), PR (ms), QRS (ms), QT (ms), QTcF (ms), QTcB (ms), and RR interval (ms). Observed values and changes from baseline for ECG parameters will be summarized by treatment group at each visit and time point.

Investigator reported ECG result will be tabulated by visit and worst-case post-baseline. In addition, the shifts from baseline to each visit and worst-case post-baseline will be summarized. Worst case post-baseline will be based on the worst observed value on or after the treatment start date. Categories will include within normal limits, abnormal without clinical significance, and abnormal with clinical significance.

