Lymphocyte subsets in peripheral blood mononuclear cells (Cohorts 1 and 2 only) ^{22,26}		X						X		
Sample for storage ^{22,27}		X						X	X	
Spot urine sample collection for:										
Exploratory PD biomarkers ²²		X						X	X	
Study Drug Administration										
Randomization		X ²⁸								
Study drug dispensation		X			X	X				
Study drug administration		QD PO from Day 1 through Week 12								
Study drug accountability				X	X	X	X	X		

Table footnotes appear on the following page.

- 1 Baseline evaluations are to be performed pre-dose, unless otherwise specified.
- 2 At the time of this amendment, subject participation in the 25 mg cohort is complete, with participation in the 50 mg cohort fully enrolled but with subject participation ongoing. The Sponsor notes that the COVID-19 pandemic may impact the conduct of the 50 and 75 mg cohorts, with challenges potentially arising from quarantines and travel limitations affecting study subjects as well as clinic and imaging facility closures. Accordingly, safety assessments scheduled for the Week 12 and 16 visits, including sample collection for clinical laboratory tests, physical examinations, and documentation of AEs, may be performed at an alternate study center or by home health care visit. Furthermore, if the subject is unable to attend the Week 12 visit at the study center, one MRI-PDFP may be performed at any time between Week 11 and 16. If this scan is performed after Week 12, the subject must continue to receive study drug until the final scan is performed; however, study drug is not to be continued for >16 weeks. The safety of subjects who continue dosing beyond 12 weeks will be assessed during this continued dosing period by planning for blood sample collection at an alternate site or home visit at Week 12 and blood sample collection and physical examination on the last day of dosing. A 4-week off treatment safety assessment is to occur after the last dose, regardless of whether a subject receives treatment for 12 or 16 weeks.
For subjects in Cohort 3, Week 16 assessments may serve as screening assessments if within the window before the Day 1 visit.

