- 3 Serum beta-human chorionic gonadotropin (β -HCG) pregnancy testing is to be performed for all female subjects of child-bearing potential during screening and serum or urine β -HCG pregnancy testing is to be performed within 48 hours before first dose on Day 1; subjects with positive results are not eligible for study participation. Pregnancy testing is to be repeated during the study any time pregnancy is suspected; study drug is to be discontinued for any subject with a positive result.
- 4 Results of liver biopsy conducted within 24 months before randomization, with findings consistent with NASH diagnosis, must be collected and documented.
- 5 If prior biopsy was not performed or is not available, subjects must have a suspected diagnosis of NASH based on clinical presentation/historical assessments (see protocol [Section 8.2](#)) and must have MRE ≥ 2.5 kpa (Cohorts 1 and 2 only) and MRI-PDFP $\geq 8\%$ during screening.
- 6 Screening serologies include HIV RNA, HBsAg, anti-HCV, and HCV RNA. Subjects with positive anti-HCV who test negative for HCV RNA at screening will be allowed to participate in the study. A PCR test for SARS-Cov-2 (the virus that causes COVID-19) also is to be performed; subjects with positive results are not eligible for study participation.
- 7 ECGs are to be performed before and 4 hours after the first study drug dose on Day 1.
- 8 Vital signs include oral temperature and supine pulse, systolic/diastolic blood pressure, and respiration rate. Measurements are to be made after the subject has been resting in a supine position for a minimum of 5 minutes.
- 9 Slit lamp and near and far visual acuity testing is to be performed. Baseline examinations may be performed within 28 days before Day 1. If a subject experiences a treatment-emergent ophthalmologic abnormality, an ophthalmologic examination should be performed within 24 to 48 hours or next business day after symptom onset to evaluate the abnormality.
- 10 Hematology parameters include hemoglobin, hematocrit, platelet count, red blood cell (RBC) count, white blood cell (WBC) count with differential, and absolute neutrophil count (ANC), and prothrombin time (PT), international normalized ratio (INR), and activated partial thromboplastin time (aPTT) and fibrinogen.
- 11 Liver aminotransferases include AST and ALT. Liver aminotransferases collected as part of the clinical chemistry panel for safety are also applicable for efficacy assessments.

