12.1.3. Electrocardiogram (ECG)

Single 12-lead ECGs are to be performed for all subjects at the time points designated in [Table 2](#).

On Day 1, ECGs are to be performed before and 4 hours after the first study drug dose, with the ECG performed prior to PK blood sample collection.

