7.4. Reference Dates

- Screening date is defined as the electronic case report form (eCRF) provided date on which a subject was screened for study entry.

- Randomization date is defined as the date on which the subject is randomized to study treatment.
- Treatment start date is defined as the date of first dose of study drug (also referred to as Day 1).
- Treatment end date is defined as the date of last dose of study drug.
- The calculation of age will use the screening date as its reference date.
- Safety data, such as AEs and laboratory assessments will use the treatment start date as a reference date to assign treatment emergence.
- Study day will be based on treatment start date as a reference date.

Reference day calculations will be defined as:

- date of interest – reference date + 1 when the date of interest \geq reference date;
- otherwise, date of interest – reference date.

For example, duration of treatment is defined as treatment end date – treatment start date + 1.

If either date is missing, reference date calculations will not be performed. Date imputation will be performed as identified in Section 7.6.

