7.5. Baseline and Post-Baseline Changes

Unless stated otherwise, baseline will be based on the last non-missing value collected prior to the start of study treatment based on the treatment start date and time, if applicable. Post-baseline values will be those collected after the treatment start date and time, if applicable.

Change from baseline is defined as:

$$\text{post-baseline value} - \text{baseline value}.$$

Percentage change from baseline is defined as:

$$(\text{post-baseline value} - \text{baseline value})/\text{baseline value} \times 100\%.$$

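### The ECG worst-case rule in SAP 8.6.2 is set by date only, so it admits the pre-dose Day 1 ECG (the baseline) into the post-baseline window; minor, and fixed in one sentence

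*SAP*

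**What the plan says.** SAP 8.6.2 tabulates the investigator's ECG result in three ordered categories: normal, abnormal but not clinically significant, and abnormal and clinically significant. The result is shown by visit and as a worst case. For the worst case the section sets its own window: "Worst case post-baseline will be based on the worst observed value on or after the treatment start date". The worst case also feeds a shift table: "In addition, the shifts from baseline to each visit and worst-case post-baseline will be summarized".

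Four other places bear on that window:

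- SAP 7.4 takes the treatment start date to be the calendar date of the first dose, Day 1.
- Protocol Table 2, footnote 7, schedules two ECGs on that date: "ECGs are to be performed before and 4 hours after the first study drug dose on Day 1". Protocol 12.1.3 repeats this. Footnote 1 to the same table adds: "Baseline evaluations are to be performed pre-dose, unless otherwise specified".
- SAP 7.5 defines baseline for the whole plan: "baseline will be based on the last non-missing value collected prior to the start of study treatment".
- SAP 7.5 also defines the other side of the line: "Post-baseline values will be those collected after the treatment start date and time, if applicable".

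**The concern.** The general rule in SAP 7.5 separates baseline from post-baseline by date and time. The specific rule in SAP 8.6.2 uses the date alone. In the Table 2 safety assessments, the ECG is the one with both a pre-dose and a post-dose measurement footnoted on Day 1, so a date-only rule fails at exactly this assessment. The pre-dose tracing is dated Day 1. It therefore meets the 8.6.2 window while also being the baseline.

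Two descriptive safety outputs are at stake: the worst-case tabulation and the shift from baseline to worst case. In the first, an abnormality present before any drug was taken can appear under a post-baseline label. In the second, no subject can be shown to improve. Change from baseline in ECG findings is a listed safety endpoint (Protocol 6.4.2, SAP 4.2), so the tables should mean what their labels say. Two programmers working from the same SAP could also produce different tables.

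**Working it through.** The plan gives no figure here to reproduce. The check compares the definitions and then works out what the literal rule does to the outputs.

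**Step 1: which Day 1 ECG falls where**

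| Day 1 ECG | Under SAP 7.5 (date and time) | Under SAP 8.6.2 (date only) |
|---|---|---|
| Pre-dose | Baseline | Inside the worst-case window |
| 4 hours post-dose | Post-baseline | Inside the worst-case window |

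The rules disagree on the pre-dose record only. If that record is missing, the screening ECG becomes the baseline. It is dated before Day 1, so the problem does not arise for that subject.

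**Step 2: effect on the shift table**

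Write N for normal, A for abnormal but not clinically significant, and C for clinically significant, in that order of severity. The literal rule reports max(baseline, worst post-dose). The date-and-time rule reports the worst post-dose category alone.

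| Baseline | Worst post-dose | Literal rule reports | Altered? |
|---|---|---|---|
| N | N | N | no |
| N | A | A | no |
| N | C | C | no |
| A | N | A | yes |
| A | A | A | no |
| A | C | C | no |
| C | N | C | yes |
| C | A | C | yes |
| C | C | C | no |

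Three of the nine pairs change, and they are the three improvement pairs. Each is shown as no change, so the improvement cells are zero whatever the data. No worsening pair changes.

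**Step 3: effect on the worst-case abnormal percentage**

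Within one arm, let

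- b = share abnormal (A or C) at the pre-dose ECG,
- q = share of those who are normal at every later ECG,
- p = share of subjects normal pre-dose who have any later abnormal ECG.

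Proportion reported as worst-case abnormal:

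- literal rule: b + (1 − b)p
- date-and-time rule: b(1 − q) + (1 − b)p
- overcount: b × q

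The C-to-A pair is also misreported, but it does not enter b × q because both categories are abnormal.

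The documents give neither b nor q. Assuming b = 10–40% and q = 10–50%:

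- low end: 0.10 × 0.10 = 0.01, or 1 percentage point (0.01 × 30 = 0.3 of 30 subjects)
- middle: 0.20 × 0.30 = 0.06, or 6 points (0.06 × 30 = 1.8 of 30)
- high end: 0.40 × 0.50 = 0.20, or 20 points (0.20 × 30 = 6 of 30)

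Thirty is the planned number on active drug in each US cohort.

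**Step 4: effect on the comparison of arms**

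Use subscript 1 for active and 0 for placebo. The literal rule shifts the difference in proportions by b₁q₁ − b₀q₀. If b and q are equal in the two arms, this is zero, and the difference is (1 − b)(p₁ − p₀) under both rules. A ratio of proportions moves towards 1, because the same b × q is added to numerator and denominator. If b or q differs between arms, the difference in proportions moves as well.

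**The case against.** The strongest reply is that the sections can be read together. SAP 7.5 defines post-baseline for the whole plan, and its allowance for exceptions opens the baseline sentence, not the post-baseline one. On this view 8.6.2 picks the worst among values already classed as post-baseline, and its reference to the start date only makes clear that the 4-hour Day 1 ECG counts. The same section summarises ECG parameters by visit and time point, so the two Day 1 records should already be distinguishable. A programmer who applied 7.5 in this way would get the right table.

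That reading is possible, but it sets aside the window that 8.6.2 states for this very output in favour of the general rule. A specific definition would ordinarily be followed where it stands. So the text needs correcting. What stands of the reply is that the documents show what the wording does when followed, not that the tables were produced that way.

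The reply is right about consequence. A reader might infer that the rule dilutes any difference between arms. Step 4 shows otherwise: with equal b and q the absolute difference does not move. A reader might also infer that a drug-related ECG signal could be lost or invented. Step 2 rules that out for the shift table, because worsening is neither created nor hidden. Nor does the rule alter the result for all 117 planned subjects of Cohorts 1 and 2. It alters it only for those with an abnormal pre-dose ECG whose later ECGs are all better.

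**Conclusion.** As written, the SAP 8.6.2 window conflicts with SAP 7.5 and admits the baseline ECG as a post-baseline value. The certain consequence of the literal rule is structural: the worst case can never be better than an available Day 1 pre-dose baseline, and the improvement cells of that shift table are empty by construction.

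The numerical size is not known. The range of 1 to 20 percentage points rests wholly on assumed b and q and is illustrative. The upper end requires half of the subjects abnormal pre-dose to be normal at every later scheduled ECG, which for a completer means Day 1 at 4 hours, Day 2, and Weeks 2, 4, 8, 12 and 16.

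The reach is narrow. By-visit tabulations, by-visit shifts and the quantitative ECG parameters are untouched, so improvement remains visible by visit. Safety has no formal testing, and all safety data are listed by subject (SAP 8.5). This is a minor point, worth correcting because the error is plain in the text and easy to remove.

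**What to change.** Reword the sentence in SAP 8.6.2 so that the worst case is the worst value observed after the date and time of the first dose of study drug. Use the nominal pre-dose and 4-hour time points to separate the two Day 1 ECGs. The 4-hour ECG then counts as post-baseline and the pre-dose ECG counts only as baseline, in line with SAP 7.5.

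The time element is essential. Changing the rule merely to dates later than the start date would drop the 4-hour Day 1 ECG, which is a genuine post-dose measurement.

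The cost is one sentence in the SAP and a matching line in the table programming. No new data are needed: the protocol already schedules the two time points, and 8.6.2 already summarises by time point.

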8.6.3. Ophthalmologic Examinations

The proportion of subjects experiencing ophthalmologic abnormalities will be tabulated by visit and by treatment group. The clinical interpretation of the ophthalmologic examination will be tabulated as normal or abnormal. The worst-case post-baseline will also be summarized.

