5.1. TVB-2640

The clinical safety profile to date for TVB-2640 is based primarily on one completed uncontrolled open-label Phase 1 study in humans (Study 3V2640-CLIN-002) in 136 patients with solid tumors, 76 treated with monotherapy (at doses ranging from 60 mg/m² to a dose of 240 mg/m² (i.e., up to 600 mg) and 60 treated with TVB-2640 in combination with a taxane (paclitaxel or docetaxel).

Overall, TVB-2640 demonstrated a favorable tolerability profile. Most treatment-emergent adverse events (TEAEs) were Grade 1 or 2 in intensity, non-serious, and manageable.

As anticipated, based on nonclinical study findings, the principal toxicities associated with TVB-2640 as monotherapy were skin and ocular effects. With monotherapy, most skin events were Grade 1 or 2 in intensity, and all were non-serious.

The maximum tolerated dose (MTD) of TVB-2640 monotherapy in patients with solid tumors was determined to be 100 mg/m². Dose-limiting toxicities (DLTs) associated with TVB-2640 monotherapy were skin and ocular events, including corneal edema, keratitis, and palmar-plantar erythrodysesthesia (PPE) syndrome.

As monotherapy, the most common individual TEAEs were alopecia (61%), PPE syndrome (46%), fatigue (37%), decreased appetite (26%), and dry skin (22%).

When TVB-2640 was administered in combination with a taxane (paclitaxel or docetaxel), skin and ocular effects also were common. Most skin events were Grade 1 or 2 in intensity, and all but 1 skin event were non-serious.

As was the case with monotherapy, the MTD of TVB-2640 in combination with paclitaxel was determined to be 100 mg/m². DLTs associated with TVB-2640 in combination included PPE syndrome and uveitis. The most common TEAEs with TVB-2640 in combination with paclitaxel were fatigue (53%), alopecia (46%), PPE syndrome (46%), nausea (40%), and peripheral neuropathy (36%). Peripheral neuropathy is known to be associated with paclitaxel.

When TVB-2640 was administered in combination with paclitaxel, 6 episodes of serious pneumonitis were experienced by 5 patients, with all assessed by the Investigator as related to both TVB-2640 and paclitaxel. (No cases of pneumonitis were reported among monotherapy patients.) Given the occurrence of these events, respiratory events were identified as adverse events of special interest for patients receiving TVB-2640 in combination.

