4.2. Safety

Safety endpoints are:

- Proportion of subjects experiencing treatment-emergent adverse events (TEAEs), Grade 3 or 4 TEAEs, and serious adverse events (SAEs).
- Change from baseline in vital sign measurements, 12-lead ECG findings, and clinical laboratory test results.
- Proportion of subjects experiencing treatment-emergent ophthalmologic abnormalities.

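### SAP 8.6.3 tabulates any ophthalmologic abnormality with no baseline reference, so its table does not estimate the treatment-emergent endpoint named in SAP 4.2 and Protocol 6.4.2

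*SAP*

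**What the plan says.** The endpoint in SAP 4.2 is: "Proportion of subjects experiencing treatment-emergent ophthalmologic abnormalities". Protocol 6.4.2 has the same wording. Neither document defines the term for an examination finding.

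The analysis in SAP 8.6.3 has three parts:

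- It opens with "The proportion of subjects experiencing ophthalmologic abnormalities will be tabulated by visit and by treatment group".
- Each examination is then reduced to a two-level reading, normal or abnormal.
- A summary of each subject's worst result after baseline completes the section.

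The section gives no baseline comparison, no rule for emergence or worsening, and no denominator. The ECG section just before it (SAP 8.6.2) does refer to baseline: "In addition, the shifts from baseline to each visit and worst-case post-baseline will be summarized". It also uses three result categories, which separate abnormal findings with and without clinical significance.

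A pre-dose eye examination exists. Protocol Table 2 schedules one at screening, and its footnote 9 says: "Baseline examinations may be performed within 28 days before Day 1". On the toxicity, Protocol 5.1 reports from the solid-tumor study: "Dose-limiting toxicities (DLTs) associated with TVB-2640 monotherapy were skin and ocular events, including corneal edema, keratitis, and palmar-plantar erythrodysesthesia (PPE) syndrome".

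**The concern.** The endpoint asks which subjects developed an eye abnormality on treatment. The planned table asks which subjects have one at a visit, or at their worst visit after baseline. The two differ for any subject who was already abnormal before the first dose.

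Such subjects can be enrolled. Exclusion criterion 22 (Protocol 8.3) bars clinically significant findings, which leaves room for minor ones. The slit-lamp examination (Protocol 12.1.4) also covers the eyelids, conjunctiva, iris and lens, and entry has no upper age limit. A stable minor finding in one of these structures could be recorded as abnormal throughout.

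Safety is one of the two primary objectives, and ocular effects are an expected harm of this drug. The examination-based endpoint should therefore measure what it is named for.

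**Working it through.** **Step 1: compare the sections.**

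- Laboratory data (SAP 8.5.2): changes from baseline and shift tables.
- Vital signs (SAP 8.6.1): changes from baseline.
- ECG (SAP 8.6.2): changes from baseline, and shifts to each visit and to worst case.
- Eye examination (SAP 8.6.3): by visit and worst case, with no baseline reference.
- Physical examination (SAP 8.6.4): listed only.

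The eye examination is thus the only one of the tabulated assessments without a baseline reference. SAP 9, which records departures from the protocol, lists no change to this endpoint.

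**Step 2: the plan's own figure.** SAP 8.6.3 states none. The nearest is in SAP 3.3: at least a 95% probability of seeing one or more adverse events among 30 subjects at a true rate of 10%. It reproduces: 1 − 0.9^30 = 0.958. It does not address baseline abnormality.

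**Step 3: illustrate the size.** The documents give neither a baseline prevalence nor ocular event rates in this population, so all inputs here are assumptions. Let b be the share of each arm abnormal before dosing and still abnormal afterwards. Let p be the rate of new abnormality among those normal at baseline.

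- Any abnormality, as in 8.6.3: b + (1 − b)p
- Treatment-emergent, over all subjects: (1 − b)p
- Treatment-emergent, over those normal at baseline: p

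With p = 10% on active and 2% on placebo:

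| b | Any abnormality | Risk ratio | Treatment-emergent, all subjects | Risk ratio | Risk difference, either count |
|---|---|---|---|---|---|
| 0% | 10.0% v 2.0% | 5.0 | 10.0% v 2.0% | 5.0 | 8.0 points |
| 10% | 19.0% v 11.8% | 1.6 | 9.0% v 1.8% | 5.0 | 7.2 points |
| 20% | 28.0% v 21.6% | 1.3 | 8.0% v 1.6% | 5.0 | 6.4 points |
| 30% | 37.0% v 31.4% | 1.2 | 7.0% v 1.4% | 5.0 | 5.6 points |

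For example, at b = 20% the active proportion is 0.20 + 0.80 × 0.10 = 0.28, and the placebo proportion is 0.20 + 0.80 × 0.02 = 0.216. The ratio is 0.28/0.216 = 1.3.

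The risk difference is (1 − b)(p1 − p0) for both counts, because b cancels. Among subjects normal at baseline it stays at 8.0 points.

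**Step 4: vary the rates.** With 30% v 5%, the tabulated risk ratio is 6.0, 3.4, 2.6, 1.8 and 1.5 at b = 0%, 5%, 10%, 20% and 30%. The direction is the same, and the ratio moves even at a low prevalence.

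**Step 5: equal differences are not equally informative.** Take 30% v 5%, b = 20% and 30 subjects per arm. Both counts have an expected difference of 20 points. The chance of p ≤ 0.05 on a two-sided Fisher test is 28% for any abnormality and 45% for the treatment-emergent count over all subjects. This only gauges the added noise, as no safety test is planned.

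**The case against.** A reader might infer that the SAP counts eye abnormalities regardless of baseline and so dilutes the signal for a known dose-limiting toxicity. The documents do not support that, for these reasons:

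- SAP 8.6.3 is silent on baseline; it does not say that baseline is to be ignored. A by-visit table can include the screening visit and show the pre-dose rate in each arm.
- Under SAP 8.5.1, a clinically significant finding that represents a change from baseline is an adverse event. All adverse event summaries are of treatment-emergent events. A new case of keratitis or corneal edema considered clinically significant would appear there by system organ class and preferred term.
- Exclusion criteria 21 and 22 limit pre-existing findings. On one reading, criterion 21 bars any history of corneal abnormality.
- The documents do not say how a minor, stable finding is classified on the normal/abnormal scale.
- The dose-limiting events arose in patients with solid tumors at 60 to 240 mg/m². In the 12 metabolic-syndrome subjects given 50 to 150 mg for 10 days, all treatment-emergent events were Grade 1 (Protocol 5.1).
- The risk difference is the same as for a treatment-emergent count over all subjects.
- The only table list in the reviewed text is the Cohort 3 addendum's. A suitable eye table for Cohorts 1 and 2 cannot be ruled out.

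Most of this stands, and it limits the point. It does not remove the mismatch. Screening rates by arm cannot show which subjects changed. The adverse event route is a separate endpoint in Protocol 6.4.2, and it rests on an investigator's judgement of significance made without blinding (Protocol 9.9). A table title alone would still need a definition of emergence. Table 14.3.20 in the addendum is restricted to clinically significant abnormalities. It therefore matches neither the endpoint nor 8.6.3, and it covers an uncontrolled cohort.

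**Conclusion.** The mismatch is in the text and needs no assumption: the endpoint is treatment-emergent, and the analysis section applies no such restriction. Followed as written, the table does not estimate the endpoint.

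The consequence is confined to the examination-based endpoint and to how it is read, since safety analyses are descriptive. Whether the effect is material is unknown. It is zero if no subject has a pre-existing abnormality. Under the assumed rates of 10% v 2%, the tabulated risk ratio falls from 5 to between 1.6 and 1.2 at prevalences of 10% to 30%. The risk difference does not depart from that of a treatment-emergent count over all subjects. These figures also assume the same prevalence in both arms and that pre-existing findings persist.

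**What to change.** In SAP 8.6.3:

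1. Define a treatment-emergent ophthalmologic abnormality as one absent at the last pre-dose examination, or worsened from it. This fits the general baseline rule in SAP 7.5.
2. Where the eCRF data allow, use the three categories of SAP 8.6.2: normal, abnormal without clinical significance, abnormal with clinical significance. Worsening cannot be derived from a normal/abnormal scale. If only that scale was collected, say so and count new abnormalities alone.
3. Report the proportion by arm over all safety-population subjects with a baseline and a post-baseline examination. Report it also over those normal at baseline. The first denominator leaves the expected risk difference unchanged and restores the ratio; the second restores both.
4. Add shift tables from baseline to each visit and to worst case post-baseline, as in SAP 8.6.2.

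The cost is one definition and one or two descriptive tables. The screening and on-study eye examinations are already collected, so no new assessment is needed.
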